| Overnight Stay                             |                                    | X                      |                         | X                      |                         |                              | X                      |                         |   |   |
| Integrative Therapy Session                |                                    |                        | X                       |                        | X                       |                              |                        | X                       |   |   |
| 7 days Integrative Telephone Contact       |                                    |                        | X G          |                        | X G          |                              |                        | X G          |   |   |
| AEs Requiring Medical Attention            | X                                  | X                      | X                       | X                      | X                       | X                            | X                      | X                       | X   |   |

Long Term Follow up after Stage 1 or Stage 2

|  |   |                  |                  |                  |                  |                |                  |                  |                |                |
|--|---|------------------|------------------|------------------|------------------|----------------|------------------|------------------|----------------|----------------|
| Spont. Reported Reactions G and all AEs |   | X                | X G   | X                | X G   |                | X                | X G   |                |                |
| Changes in Tinnitus and/or Pain                    |   | X D,1 | X D,1 | X D,1 | X D,1 | X I | X D,1 | X D,1 | X I | X I |
| AEs of psychiatric status or withdrawal            | X | X                | X                | X                | X                | X              | X                | X                | X              | X              |
| Serious Adverse Events                             | X | X                | X                | X                | X                | X              | X                | X                | X              | X              |
| Perception of Third Session                        |   |                  |                  |                  |                  | X              |                  |                  | X              |                |
| Complete Stage 2, go to 1yr F/U                    |   |                  |                  |                  |                  |                |                  |                  | X              |                |
| RRPQ   |   |                  |                  |                  |                  |                |                  |                  | X              |                |
| Issue Memory Aid Card                              |   |                  |                  |                  |                  |                |                  |                  | X              |                |
| Follow-up Questionnaire                            |   |                  |                  |                  |                  |                |                  |                  |                | X              |
| Termination Visit                                  |   |                  |                  |                  |                  |                |                  |                  |                | X              |

\* If Visit 19 is more than 8 weeks after V13 then the measures from V13 will need to be repeated prior to starting Stage 2 A =First session is 1 day after Exp session B =Approximately 6 hours post MDMA C =At the beginning of the session D =As needed E =Approximately every 60 minutes F = Given on 2nd integrative session only G = For 7 days post Exp. Session, C-SSRS D2 and D7 of calls only, General well being for all 7 days H=CAPS may be videotaped I= Only in subjects with pre-existing tinnitus and/or chronic pain.

## **5.0 Randomization and Blinding**

This is a randomized, triple-blind, dose response study with an open-label cross-over segment. For Stage 1, a randomization list will be prepared at the beginning of the study. If needed, subsequent randomization lists will be created to replace subjects who withdraw from the study to ensure that replacement subjects are not added to the end of the initial list. Each subject will be assigned to one of the three dose conditions; 30 mg (low dose), 75 mg (medium dose) or 125 mg (full dose). Twelve evaluable subjects will be assigned to the full dose condition, six evaluable subjects to the 75 mg condition and six evaluable subjects to the 30 mg low dose condition. The study will employ a blinded randomization procedure that will maintain the 2:1:1 ratio while maintaining the blind and ensuring that each subsequent condition assignment is not predicated on the previous assignment.

## **6.0 Sample Size and Power Considerations**

This study is a pilot investigation intended to gather preliminary data on the safety and efficacy of MDMA in 24 evaluable veterans, firefighters, or police officers with chronic, treatment-resistant PTSD. Because of their exploratory nature, pilot studies are often not powered for detecting the desired effect. Because it is a pilot study in a small sample, results will be used to collect effect size estimates for statistical power calculations for adequately powered subsequent studies.

## **7.0 Measures**

### **7.1 Outcome Measures**

Clinician-Administered PTSD Scale (CAPS-4) Global Severity Score, Diagnostic Criteria Met score

Global Assessment of Functioning (GAF), total score

Beck Depression Inventory-II (BDI-II), total score

Post Traumatic Growth Inventory (PTGI), total

Dissociative Experiences Scale-II (DES-II), total

Pittsburgh Sleep Quality Index (PSQI), total score

NEO Personality Inventory (NEO PI), five factors

States of Consciousness Questionnaire (SOCQ), total and composite scores

Long-term Follow-up Questionnaire (LTFU Questionnaire)

## **7.2 Safety Measures**

Columbia Suicide Severity Rating Scale (C-SSRS)

Subjective Units of Distress (SUD)

General Well-being (GWB)

Visual analog scale for Tinnitus and/or Pain visual analog scale

Vital signs (systolic blood pressure (SBP), diastolic blood pressure (DBP), heart rate (HR), body temperature (BT))

Adverse Events (AE), including Spontaneously Reported Reactions (SRR)

## **7.3 Process Measures**

Therapist Adherence Criteria

Belief of Condition Assignment

Subject perceptions of experimental sessions

Reactions to Research Participation Questionnaire (RRPQ)

## **8.0 Analyses**

In general, nominal variables will be described in terms of frequencies and percentages and analyzed using chi square analysis. Ordinal and non-normal continuous variables will be described using sample median and range, and analyzed by non-parametric statistical tests, and approximately normal variables will be described using sample mean and standard deviations and analyzed by parametric statistical tests. All statistical tests will be two-sided and a difference resulting in a p-value of less than or equal to 0.05 will be considered statistically significant. All p-values will be rounded to and displayed in four decimals. If a p-value less than 0.0001 occurs it will be shown in tables as <0.0001.

Clinical data will be presented in tabular format. Data not subject to analysis according to this plan will not appear in any tables or graphs, but will be included in the data listings.

Analyses will be carried out with SAS Version 9.3 or higher. Selected results may be presented graphically using standard graphical software.

Post-hoc exploratory analyses not identified in this SAP may be performed to further examine the study data. These analyses will be clearly identified as such in the final clinical study report.

## 8.1 Analysis Populations

*Intent-to-treat (ITT)*: all subjects who were randomized

*Per protocol (PP)*: all subjects who completed Stage 1, underwent assessment of PTSD symptoms, and did not experience a major protocol deviation

*Crossover*: all subjects who completed Stage 2 in addition to completing Stage 1

*Safety*: all subjects who receive any study treatment

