## 5.2 Randomization and Subject Numbering

This is a randomized, triple-blind, dose comparison study with an open-label cross-over segment. For Stage 1, a randomization list will be prepared at the beginning of the study. Another list will be created to replace subjects who withdraw from the study and are unblinded. Each participant will be assigned to one of the three dose conditions; 30 mg (low dose), 75 mg (medium-dose) or 125 mg (full dose). Twelve participants will be assigned to the full-dose condition, six participants to the 75 mg condition and six participants to the 30 mg low dose condition. The study will employ a blinded randomization procedure that will maintain the 2:1:1 ratio while maintaining the blind and ensuring that each subsequent condition assignment is not predicated on the previous assignment. Drug containers will be assigned a unique random number. At least 24 hours before each experimental session, container assignments to each subject will be performed on a per experimental session basis, and the container will contain the initial and supplemental capsules for a single experimental session. This will be done by contacting the Randomization Monitor or logging into the web-based randomization system. The unblinded Randomization Monitor will also oversee drug encapsulation and labeling of drug bottles. Replacement doses for subjects who replace dropouts that retain the same ratio of condition assignment will also be created. The Randomization Monitor will provide the investigators with sealed envelopes that will permit emergency unblinding for an individual subject if required. In all other cases, the blind will be maintained up through the primary endpoint assessment. The participant, independent rater and both investigators conducting psychotherapy will be blind to condition assignment, until that point. Participants who drop out of the study or are withdrawn by the Clinical Investigator prior to the primary endpoint will be replaced until blinded data has been collected from 24 participants. Subjects who withdraw during Stage 2 or during the long-term follow-up portion of the study will not be replaced.

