# 6.2.11 Assessment Two Months after Third Open-Label Session (End of Stage 2)

All participants in Stage 2 will be assessed by the independent rater two months after their final open-label session. At that visit, the independent rater will administer the CAPS, which may be recorded to video, and assess participants on the GAF, and participants will complete the BDI-II, PTGI (in reference to the start of the study), PSQI, DES-II, and NEO-PI. Participants will also complete C-SSRS and RRPQ with the therapists. Participants will provide their perception of the experimental sessions. Adverse Events and medications will be collected as described in Sections 8 and 9 of the protocol. The visual analog scale will be used to collect changes in pre-existing tinnitus and chronic pain symptoms.

Subjects will receive a memory aid card for use between this visit and the 12-month follow up. Subjects will use this card to record AEs, medications, and changes in psychiatric status that they will be asked about at the termination visit. Memory aids will not be collected. Subjects may return to taking psychiatric medications from this point onward if necessary.

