| Visit #                                    | Preparatory Session                | Experimental Session 1 | Integrative Sessions    | Experimental Session 2 | Integrative Sessions    | Secondary endpoint           | Experimental Session 3 | Integrative Sessions    | End of Stage 2 & Outcome                  | 1 Year Follow-up                                  |
| Type of Visit                              | Within maximum of 5 months of V13* | After V19              | Before V24 A | 3-5 weeks post V20     | Before V28 A | 1 month post V24, before V29 | 3-5 weeks post V24     | Before V33 A | May happen over > 1 day 2 months post V29 | Follow-Up & Outcome                               |
| Visit Timing or Study day or Window        |                                    |                        |                         |                        |                         |                              |                        |                         |   | May happen over > 1 day. One Year post V14 or V29 |
| Confirm Informed Consent                   | X                                  |                        |                         |                        |                         |                              |                        |                         |   |   |
| Confirm Inclusion/Exclusion                | X                                  |                        |                         |                        |                         |                              |                        |                         |   |   |
| Enrollment in Stage 2                      | X                                  |                        |                         |                        |                         |                              |                        |                         |   |   |
| Collect Concomitant Medication             | X                                  | X                      | X                       | X                      | X                       | X                            | X                      | X                       | X   | X   |
| Record to Audio/Video                      | X                                  | X                      | X                       | X                      | X                       | X H               | X                      | X                       | X H                            |   |

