#### Crossover Subject Analyses

Data from subjects assigned to the low and medium dose groups, i.e. ‘crossover population,’ will be analyzed by within-subject t-tests comparing difference scores from primary endpoint in Stage 1 to secondary endpoint in Stage 2 (Table 3 and 4). The following measures total scores will be analyzed in this fashion: CAPS, PTGI, BDI-II, GAF, PSQI, DES-II, and NEO PI.

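### The SAP restricts the crossover population to Stage 2 completers, but the crossover test ends before Stage 2 does, so a subject with both required scores could be excluded for what happens afterwards

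*SAP*

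**What the plan says.** - **Population.** SAP 8.1 defines Crossover as "all subjects who completed Stage 2 in addition to completing Stage 1".
- **Test.** SAP 8.9.2.2 (Crossover Subject Analyses) specifies within-subject t-tests "comparing difference scores from primary endpoint in Stage 1 to secondary endpoint in Stage 2" for CAPS, PTGI, BDI-II, GAF, PSQI, DES-II and NEO PI. It identifies the population differently: "Data from subjects assigned to the low and medium dose groups, i.e. ‘crossover population,’ will be analyzed by within-subject t-tests". No completion condition is repeated there.
- **Timing of the secondary endpoint.** The Stage 2 Time and Events table in the SAP places V28 at "1 month post V24, before V29", that is, before the third session.
- **Timing of Stage 2 completion.** The same table marks "Complete Stage 2, go to 1yr F/U" in the End of Stage 2 column. SAP 8.9.2.2 (Long-term Follow-up) identifies End of Stage 2 as visit 33. Protocol 6.2.11 fixes its timing: "All participants in Stage 2 will be assessed by the independent rater two months after their final open-label session".
- **Numbers.** SAP 5.0 plans "six evaluable subjects to the 75 mg condition and six evaluable subjects to the 30 mg low dose condition". Protocol 5.2 adds: "Subjects who withdraw during Stage 2 or during the long-term follow-up portion of the study will not be replaced".

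**The concern.** The test needs two measurements, V13 and V28. The population in which it is run requires something later, completion of Stage 2. Whether a subject counts therefore depends on events after the outcome was recorded, although nothing the test needs is missing.

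Two things are at stake. The first is precision: the set is small, and Stage 2 withdrawals are not replaced. The second is possible selection: if those who stop after V28 tend to be those who did less well, the open-label improvement is estimated in a favourable subset. This matters because SAP 6.0 says the pilot is meant to supply effect-size estimates for later studies, and Protocol 12.0 lists the secondary endpoint among the time points at which effect sizes are to be estimated.

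The mismatch between 8.1 and 8.9.2.2 also means that two programmers could each follow the SAP and report different numbers of subjects for the same test.

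**Working it through.** The documents give no power, SD, effect size or attrition rate for this test, so there is no stated figure to reproduce. The check has two parts.

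**1. The definition against the schedule**

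| Element | Needs data up to |
|---|---|
| Crossover test (SAP 8.9.2.2) | V28, before session 3 (V29) |
| Crossover population (SAP 8.1), with completion as marked in the schedule | V33, two months after session 3 |
| Session 3 comparison (SAP 8.9.2.2, 3 vs. 2 sessions) | V33 |

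A subject who stops between V28 and V33 meets the data requirement of the first row but not the condition in the second. No other rule clearly brings that subject back:

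- The early-termination rule in SAP 8.2 is worded for ITT and Safety variables and does not name Crossover.
- Protocol 6.3 asks, after discontinuation, for the primary-endpoint and 12-month evaluations where they can be obtained. It does not list the end-of-Stage-2 visit, which is itself timed from session 3.

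**2. Size, under assumptions**

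Maximum n: 24 subjects allocated 2:1:1 gives 12, 6 and 6, so at most 6 + 6 = 12 can cross over.

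Chance that the definition has any effect: if each subject stops between V28 and V33 with assumed probability q, P(at least one excluded) = 1 − (1 − q)^12.

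| Assumed q | Expected number excluded (12q) | P(at least one) |
|---|---|---|
| 5% | 0.6 | 46% |
| 10% | 1.2 | 72% |
| 15% | 1.8 | 86% |
| 20% | 2.4 | 93% |

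Precision: the 95% half-width for the mean change, in SDs of the change, is t(0.975, n − 1)/√n.

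Bias: 200,000 simulated sets of 12 normally distributed changes, with the k subjects ranking worst on a factor correlated ρ with the change excluded. Bias is in SDs of the change, and positive means improvement is overstated. Type I error is the rejection rate of the two-sided 0.05 paired test when the true mean change is zero.

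| Excluded (k) | n | Half-width | Bias, ρ = 0 | Bias, ρ = 0.5 | Bias, ρ = 1 | Type I error, ρ = 0 / 0.5 / 1 |
|---|---|---|---|---|---|---|
| 0 | 12 | 0.635 | 0 | 0 | 0 | 5% |
| 1 | 11 | 0.672 | 0 | +0.08 | +0.15 | 5% / 6.0% / 9.8% |
| 2 | 10 | 0.715 | 0 | +0.14 | +0.28 | 5% / 7.5% / 19.0% |
| 3 | 9 | 0.769 | 0 | +0.20 | +0.39 | 5% / 9.3% / 30.8% |

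With two excluded, the interval widens by 0.715/0.635 = 1.126, or about 13%. The bias should scale with ρ, and it does: 0.5 × 0.275 = 0.138 for k = 2, against 0.138 simulated. If the best responders stop instead, the sign of the bias reverses by symmetry.

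**The case against.** Four points on the other side carry weight.

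- **The exclusion is conditional.** It requires that someone stops between V28 and V33, that completing Stage 2 means reaching V33, and that 8.1 governs over the wording in 8.9.2.2. The SAP has no written definition of completion; V33 is the schedule's marker. This stands, and it means that a possible exclusion has been shown and not an actual one.
- **The 8.9.2.2 wording may only say which arms can enter Stage 2.** That is plausible: taken as a definition, it would include subjects who declined Stage 2 and have no V28. But then 8.1 governs and the restriction applies. If instead it is a competing definition, the two sections conflict. Either way the text needs reconciling.
- **A completer set has a proper use.** The V28-to-V33 comparison of three against two sessions needs V33 data. This stands, but it does not justify dropping complete V13–V28 pairs from a different test.
- **The stakes are limited.** This is an uncontrolled, open-label comparison in a pilot. SAP 3.2 lists it among exploratory objectives, although 8.9.2.2 places it under secondary analyses. SAP 8.9 also promises descriptive statistics by treatment group without restricting them to Crossover, so V28 scores need not vanish from the report. This stands and lowers the severity.

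A reader might go further and infer that the plan necessarily inflates open-label improvement. The documents do not support that, because they give neither a Stage 2 attrition rate nor reasons for stopping after V28, and a subject could stop because of improvement. One can construct a case in which 2 of 12 stop with no change and 10 improve by 25 CAPS points. The completer mean is then −25.0 against (10 × −25 + 2 × 0)/12 = −20.8. But the 20% excess is simply 12/10 = 1.2, fixed by the chosen inputs, and says nothing about this trial.

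**Conclusion.** The mismatch is real, and its severity is minor. As written, 8.1 makes inclusion in a test that ends at V28 depend on completing Stage 2 afterwards, and 8.9.2.2 describes the same named population in terms that do not match.

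The consequence depends on what happens between V28 and V33:

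- If nobody stops, nothing changes.
- If subjects stop for reasons unrelated to response, the cost is precision only.
- Improvement is overstated only if stopping goes with poor response. The worst-responder figures above are an extreme bound and not an expectation.

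These sizes rest on assumed attrition, normally distributed changes and a full crossover set of 12. The primary comparison at V13 does not use the Crossover population and is untouched.

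**What to change.** Amend the SAP wording as follows:

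1. In 8.1, define Crossover as low- and medium-dose subjects who receive at least one Stage 2 dose.
2. In 8.9.2.2, run the V13-to-V28 test on all of these who have both a Stage 2 starting value and a V28 assessment. State which starting value applies when V19 falls more than 8 weeks after V13: the schedule then requires the V13 measures to be repeated, and Protocol 6.2.10 treats the repeat as a new baseline.
3. Report how many Crossover subjects lack V28. The revised set still omits those who stop before that visit, so selection is reduced and not removed.
4. Keep Stage 2 completers as a separately named set, for analyses that need V33 and as a sensitivity analysis of the V13-to-V28 test.
5. Make the population wording in 8.1 and 8.9.2.2 agree.

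This is a free improvement: no new visits, data or procedures are needed.

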## 8.2 Handling of Dropouts, Missing Data

Early termination visit data for ITT and Safety variables will be analyzed at the closest scheduled visit. If the closest visit has valid data, the early termination data will be assigned to the next available visit. If a subject discontinues and does not participate in an early termination visit, data from the last available visit will be used to replace the missing early termination visit data.

Subjects who discontinue treatment prior to completing the second experimental session prior to the primary endpoint will be replaced. These subjects will be asked to complete an outcome assessment prior to continuing to the long-term follow-up. These subjects will be included in the ITT population.

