## 6.3 Removal of Participants from the Study

Participants can withdraw consent at any time without prejudice. The investigator can withdraw a participant if, in his or her clinical judgment, it is in the best interest of the participant or if the participant cannot comply with elements of the protocol that are critical for safety or necessary for the scientific integrity of the study. If the investigator withdraws a participant from the study, the investigators will explain the reason for withdrawing the participant.

If a subject develops any exclusion criteria that in the opinion of the Medical Monitor, affects the safety of the subject, including psychiatric diagnosis, pregnancy or excluded medications, the subject will discontinue treatment.

Subjects will be clinically monitored after discontinuation of treatment by at least one of the therapists. The cause of discontinuation will be recorded in the subject's source records and CRF. Whenever possible, the tests and evaluations listed for the primary endpoint and 12-Month Follow Up will be carried out. Efforts will be made to obtain information about AE outcomes, if deemed necessary by the investigators, Medical Monitor and/or Sponsor.

Subjects who discontinue treatment prior to the primary endpoint will be replaced. Individuals who replace these subjects will be assigned the next available subject

number. Subjects who discontinue treatment after the primary endpoint in Stage 1 will not be replaced. If Stage 1 subjects discontinue treatment before the primary endpoint, the site should contact the randomization monitor for replacement instructions. If there is an emergency requiring knowledge of subject's condition assignment, the blind may be broken for an individual subject. The investigator will be provided with sealed emergency unblinding envelopes corresponding to each Enrollment Code. These sealed envelopes will be stored in a secure limited access area and should remain sealed if there are no emergency unblinding events during the study. The therapists, independent rater, and subject will remain blind to condition assignment until unblinding at the primary endpoint. Unblinding at the primary endpoint will be done using the web-based randomization program. Detailed instructions will be provided to the site in a separate document.

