### **8.9.2.2 Secondary Efficacy Analyses at Secondary Endpoints**

#### Assess 3 vs. 2 experimental MDMA sessions

For the CAPS, PTGI, BDI-II, GAF, PSQI, DES-II, and NEO PI, the absolute changes in the measures from the primary endpoint to end of Stage 1 for the 125 mg group will be compared with t-tests. In the crossover subjects (30 mg and 75 mg group) the absolute

changes in the measures from the secondary endpoint to end of Stage 2 will be compared with t-tests.

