#### Long-term Follow-up

For the CAPS, PTGI, BDI-II, GAF, PSQI, DES-II, and NEO PI, the absolute changes in the measures from baseline to the long-term follow-up visit (one year post final experimental year) will be compared with t-tests. The absolute changes in the measures from long-term follow-up to End of Stage 1 (visit 18, 125 mg) or long-term follow-up compared to End of Stage 2 (visit 33, 30 and 75 mg) will be compared with within-subject t-tests.

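### SAP 8.2 sets no time window or session condition for early-termination scores, so under ITT they can enter the 125 mg third-session test or stand as 12-month outcomes

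*SAP*

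**What the plan says.** SAP 8.2 handles early-termination (ET) assessments in three steps. First: "Early termination visit data for ITT and Safety variables will be analyzed at the closest scheduled visit". Second: "If the closest visit has valid data, the early termination data will be assigned to the next available visit". Third, where no ET visit takes place, "data from the last available visit will be used to replace the missing early termination visit data". The section gives no maximum interval, sets no condition on sessions received, and does not define which visit counts as next available.

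SAP 8.9.2.2 assesses the third session by the change "from the primary endpoint to end of Stage 1 for the 125 mg group will be compared with t-tests", that is, V13 to V18. For crossover subjects it uses the change from the secondary endpoint to the end of Stage 2 (V28 to V33). For long-term follow-up it tests "the absolute changes in the measures from baseline to the long-term follow-up visit", and also compares that visit with V18 or V33. No analysis population is attached to the 125 mg test or the long-term tests.

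SAP 8.1 defines ITT as everyone randomized, PP as Stage 1 completers without a major deviation, and Crossover as those who completed both stages. SAP 3.2 states the third-session objective for subjects who received that session. Protocol 6.3 adds: "Subjects who discontinue treatment after the primary endpoint in Stage 1 will not be replaced".

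**The concern.** V18 and the 12-month visit are defined by what came before them. V18 is two months after session 3, and the long-term visit is 12 months after the final session. A rule that fills these slots from whatever ET score is available, without checking exposure or elapsed time, lets a value be analysed under a label it does not fit.

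Two analyses are exposed. The V13 to V18 test is meant to show what a third session adds, and a subject who did not have one carries no information on that. The long-term tests are meant to show durability, and a score taken shortly after V18 or V33 says little about month 12. Three versus two full-dose sessions is a stated study question (SAP 2.0), and the full-dose arm has only 12 subjects, so one or two such values matter.

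**Working it through.** The documents attach no power, effect size, SD or dropout figure to this rule, so there is nothing to reproduce. The check traces the rule through the visit schedule and then illustrates the size.

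**Inputs.** V13 is 1 month after session 2 (Protocol 6.2.7). Session 3 (V14) is 3 to 5 weeks after session 2 (Time and Events table). V18 is 2 months after session 3 (Protocol 6.2.8). Long-term follow-up is 12 months after the final session (Protocol 6.2.12). The 125 mg group has n = 12, and tests are two-sided at 0.05 (SAP 5.0, 8.0). A month is taken as 30.4 days. A scheduled visit is read as one where the measure is due.

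**Step 1: a full-dose subject with V13 done and no session 3.** In months from session 2:
- V13 = 1.
- Planned V14 = 21/30.4 to 35/30.4 = 0.69 to 1.15.
- Planned V18 = V14 + 2 = 2.69 to 3.15.
- V13 to V18 gap = 1.69 to 2.15, with its midpoint 0.85 to 1.08 months after V13.

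Before the midpoint, an ET score is closest to V13. V13 is already filled, so the score moves to V18. After the midpoint, V18 is itself closest, until the 12-month visit becomes closer. Either route puts a two-session score in the V18 slot. If there is no ET visit, the V13 value stands in as the ET value. If that is dated in the same period it follows the same route, with a change of exactly zero.

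**Step 2: a subject who leaves after V18 or V33.** The gap to long-term follow-up is 12 − 2 = 10 months, with its midpoint at 5. An ET score taken t months after V18 or V33, with t below 5, is closest to a filled visit and moves to the 12-month slot, early by 10 − t, that is, 5 to 10 months. With t = 2, the score is from month 2 + 2 = 4 after the last session and is analysed as month 12, 8 months early. Past the midpoint, the first step alone places it there, up to 5 months early. For a low- or medium-dose subject who declines Stage 2, the gap from V13 is 12 − 1 = 11 months.

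**Step 3: size in the 125 mg third-session test.** Assume that k of the 12 had no session 3 and that their mean change is zero. The mean change is then multiplied by (12 − k)/12: 0.917 for k = 1, 0.833 for k = 2, 0.75 for k = 3.

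**Step 4: power illustration.** Assume a standardized change dz among those who had session 3. With the k subjects excluded, power comes from the noncentral t with 11 − k df and noncentrality dz·√(12 − k). The mixed samples were simulated 200,000 times, with the k changes either exactly zero (carried forward) or mean 0 and SD 1 (real ET scores).

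| dz | k | No dropouts | Zeros kept | ET scores kept | Excluded |
|---|---|---|---|---|---|
| 0.5 | 2 | 0.35 | 0.29 | 0.25 | 0.29 |
| 0.8 | 1 | 0.71 | 0.66 | 0.62 | 0.67 |
| 0.8 | 2 | 0.71 | 0.61 | 0.52 | 0.62 |
| 1.0 | 2 | 0.88 | 0.80 | 0.70 | 0.80 |

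Under these assumptions, keeping such scores never gives more power than leaving them out, and it also biases the mean.

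**The case against.** The other side has several sound points.

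- **The objective already restricts the test.** SAP 3.2 limits the third-session comparison to subjects who received the session. That stands as intent, but 8.9.2.2, which a programmer would follow, does not repeat it.
- **Scope.** The rule covers ITT and Safety variables only, and a PP analysis would exclude full-dose subjects who did not complete Stage 1. The error is therefore permitted, not certain.
- **Crossover subjects.** A reader might infer that V28 to V33 is diluted in the same way. The Crossover population in SAP 8.1 requires completing Stage 2, so using it protects that test. The protection is not fully secure, because the crossover paragraph of 8.9.2.2 describes the population more loosely, as those assigned to low and medium dose.
- **Elapsed time.** A reader might infer that scores move forward whatever the timing. They do not: proximity is applied first, and a score moves only if the closest visit is filled. What is missing is an upper limit.
- **Scores before V13.** Read literally, an ET CAPS could be filed at an integrative visit and lost to the V13 analysis. That reading is strained. No CAPS is due at V6 to V12, the valid-data test makes sense only where the measure is collected, and SAP 8.3 has ITT use all available data.
- **Frequency.** Neither Time and Events table schedules an ET CAPS after V13, and Protocol 6.3 seeks the 12-month evaluation whenever possible. A subject who attends month 12 has a real value there.
- **Weight.** SAP 3.2 lists these objectives as exploratory, and SAP 6.0 says this is a pilot. That limits the severity, but SAP 8.9.2.2 still tests them formally as secondary efficacy analyses.

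**Conclusion.** The point holds for two analyses, on condition that ITT is used, which SAP 8.9.2.2 leaves open. A full-dose subject with no session 3 can be counted in the V13 to V18 test, against the SAP's own objective. An ET score from the first 5 months or so after V18 or V33 can be analysed as the 12-month result, 5 to 10 months early. The timing follows from the visit schedule. The effect on the estimate does not: about 8% per subject in the 125 mg group (17% for two) requires zero mean change in those subjects. A real ET score could show improvement or worsening, and the number of dropouts is not given. The power figures rest on the same assumption and on an assumed dz.

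The documents do not support extending this to the primary V13 analysis, nor to V28 to V33 when the defined Crossover population is used. The SAP should be changed, because a stated rule can mislabel outcomes and the correction is cheap. The harm is confined to secondary and exploratory results.

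**What to change.** In SAP 8.9.2.2, restrict the V13 to V18 and V28 to V33 contrasts to subjects who received session 3, and name the analysis population for each test, including the long-term ones. Align the description of crossover subjects there with SAP 8.1.

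In SAP 8.2, define the next available visit and assign ET data to a later visit only if all three conditions hold:
1. the measure is due at that visit;
2. the subject received the sessions that define it;
3. the ET date falls inside a stated window, which matters most for the 12-month visit.

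Otherwise list the value and leave the visit missing. The same conditions should govern V13. A blanket rule filing every post-dose score before V13 as the V13 value would bring the mislabelling into the primary analysis, since V13 is defined as one month after session 2.

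The change is to SAP wording only. It costs a few values at V18, V33 and 12 months, which remain in the listings.
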